1.16. Blood sampling

Screening visit blood will be taken for full blood count, renal function, liver function tests, glucose, clotting, and CRP. These will be processed in the Haematology and Chemical Pathology Laboratories of Imperial College Healthcare NHS Trust. Serology will be performed at pre-screening, screen, and day 28 by microneutralisation assay. Serum will also be used in future serological tests for comparison purposes.

The total amount of blood taken at screening would amount to no more than 51mL. Blood for peripheral blood mononuclear cells (PBMCs) will also be taken (see table 1). On these occasions, 20-40mls of blood will be taken (see Table 1). In addition, blood for gene expression profiling, serum and plasma will be taken (see table 1). Blood for gene expression profiling will be taken up to 2 times per day. A maximum of 70mls of blood will be taken on any single day, with a total of no more than 500mls taken between screening and the 28 day challenge period (see Table 1).

DNA processing will be taken from the residual or additional blood samples provided by the subjects

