1.10. Withdrawal criteria

Any subjects can withdraw from the study at any time if they wish to. Subjects can also be removed from the study if an investigator feels this is necessary or appropriate. Subjects will be closely monitored throughout by the study doctor. This is defined further in the section on 'Serious Adverse Events'.

If a participant loses capacity during the study, then the participant would be withdrawn from the study. Identifiable data or tissue already collected with consent would be retained and used in the study. No further data or tissue would be collected or any other research procedures carried out on or in relation to the participant.

The nature of this study design does not allow participants to be replaced after Day 0.

STUDY DESIGN

Table 1

Procedures			DAY (relative to viral inoculation)																						
	Pre-screen	Screen	-7	-3	-1	0 am	0 pm	1 am	1 pm	2 am	2 pm	3 am	3 pm	4 am	4 pm	5 am	5 pm	6	7	8	9	10	14	28	180
Consent	X	X																							
Virus inoculation						X ¹																			
PCR					X										X										
Physical Examination		X		X	X																X		X	X	
Chest X-ray		X																							
12 lead ECG		X					X				X					X			X		X		X		
Lung Function Tests		X		X	X		X		X		X		X		X		X		X	X	X	X	X	X	
Screen blood tests		40																							
Blood - serum	10					10																		10	10
Blood for HLA typing	5																								
Blood - PBMCs (mls)				20	20		30		10		30		10		10		10		40			30	10	30	20
Blood – plasma (mls)		6	6	6	10	10		10	6	10		10		10		10		6	6		6	6	6	6	
Blood – RNA (mls)		5	5	5	7.5	7.5		7.5	7.5	7.5		7.5		7.5		7.5		5	5		5	5	5	7.5	
Throat swabs			X		X	X		X		X		X		X		X		X		X	X	X	X	X	
Stool swabs					X	X		X		X		X		X		X		X	X	X	X	X	X		
Breath collection					X		X		X		X		X		X		X		X	X	X	X	X	X	
Oral swabs					X		X		X		X		X		X		X		X	X	X	X	X	X	

¹ Virus inoculation after sampling

Table 1 continued

Procedures			DAY (relative to viral inoculation)																						
	Pre-screen	Screen	-7	-3	-1	0 am	0 pm	1 am	1 pm	2 am	2 pm	3 am	3 pm	4 am	4 pm	5 am	5 pm	6	7	8	9	10	14	28	180
Nasal lavage (daily)		X	X	X	X	X		X	X	X	X	X	X	X	X	X	X	X	X	X	X	X	X	X	
Nasosorption		X	X	X	X	X		X		X		X		X		X		X	X	X	X	X	X	X	
Nasal curettage		X						X		X		X							X			X	X	X	X
Nasal brushing		X																						X	
Faros ECG sensor			X	X	X	X	X	X	X	X	X	X	X	X	X	X	X	X	X	X	X	X			
Biovotion Everion			X	X	X	X	X	X	X	X	X	X	X	X	X	X	X	X	X	X	X	X			
Insert Lumee			X																						

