1.11.3. Follow-up period (outpatient, day 11 – day 196)

Participants will return to the ICRRU or ICRF on days 14 and 28 post infection for assessment and sampling. During the 6 months after challenge, subjects will be asked to report episodes of upper respiratory tract symptoms by email to the study email address. If an episode of natural infection occurs, the subject will be invited to re-attend for blood (10mL clotted blood for serum, 40mL lithium heparin for PBMCs) and upper respiratory tract samples (nasal wash and SAMs) to be collected. After 6 months, subjects will be asked to return for further samples to be taken. Further samples will be collected at the peak of the secondary response 7 days post-infection. Table 1 summarises when each sample type will be taken.

STUDY PROCEDURES

A variety of procedures are carried out during the study period. The frequency and timing of these procedures are shown in Table 1 above. For the screening, and days -7, -3, -1, 14, 28 and 180 visits, procedures will take place in the procedures room on ICRRU, ICRF or CRC; for days -1 to 10 subjects will reside in the confinement facility and procedures will take place there (with the possible exception of virus inoculation).

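### The 500 mL blood limit in section 1.16 does not agree clearly with Table 1: the schedule totals 547.5 mL if the screening visit counts and 496.5 mL if it does not

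*Combined protocol and SAP*

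**What the plan says.** Section 1.16 (Blood sampling) makes these statements about volume, in this order:

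- Screening visit: "The total amount of blood taken at screening would amount to no more than 51mL".
- PBMC draws: 20 to 40 mL on each occasion, with a reference to Table 1. Blood for gene expression, serum and plasma is described as being in addition to this.
- Daily limit: "A maximum of 70mls of blood will be taken on any single day".
- Cumulative limit: "with a total of no more than 500mls taken between screening and the 28 day challenge period", again with a reference to Table 1.
- DNA: to come from leftover blood or from extra samples. No volume is given.

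Section 1.11.3 (Follow-up period) provides for one more draw. A participant with a natural respiratory infection in the 6 months after challenge is asked back for "10mL clotted blood for serum, 40mL lithium heparin for PBMCs", which is 50 mL.

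Table 1 gives volumes by visit in six blood rows: screening tests, serum, HLA typing, PBMCs, plasma and RNA. Under section 1.7.2 the screening visit falls between day -60 and day -7.

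**The concern.** The cumulative limit is worded as an absolute ceiling on blood taken from healthy volunteers, and it names screening as the start of the window. On the plain wording the screening visit is inside that window, and the scheduled volumes then exceed the ceiling. If the window is meant to open after screening, the schedule fits, but only just, and only if other statements in the protocol are read in particular ways.

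At stake is whether the limit can be applied at all. Staff cannot tell whether a complete schedule complies, and a monitor cannot tell whether a deviation has occurred. Anyone who omits or reduces a draw to stay under 500 mL has no rule saying which draw it should be. With at most 20 challenged participants (section 1.6), unplanned differences in sampling between participants would be unwelcome in the exploratory analyses of immune and biological readouts (section 1.5).

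**Working it through.** **Inputs.** Volumes in mL from Table 1, screening column to day 28:

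| Row | Screening visit | Day -7 to day 28 | Total |
|---|---|---|---|
| Screening tests | 40 | 0 | 40 |
| Serum (days 0, 28) | 0 | 20 | 20 |
| PBMCs | 0 | 250 | 250 |
| Plasma | 6 | 124 | 130 |
| RNA | 5 | 102.5 | 107.5 |
| **Sum** | **51** | **496.5** | **547.5** |

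The HLA sample is drawn at pre-screening. It lies outside the stated window, as do the pre-screening and day 180 serum and the day 180 PBMC draw.

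**Row sums.**

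- PBMCs: days -3, -1, 0, 1, 2, 3, 4, 5, 7, 10, 14 and 28 give 20 + 20 + 30 + 10 + 30 + 10 + 10 + 10 + 40 + 30 + 10 + 30 = 250.
- Plasma: ten draws of 6 and seven of 10 give 60 + 70 = 130. One of the 6 mL draws is at screening, so 130 − 6 = 124 fall after it.
- RNA: eight draws of 5 and nine of 7.5 give 40 + 67.5 = 107.5. One of the 5 mL draws is at screening, so 107.5 − 5 = 102.5 fall after it.

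**Step 1: reproduce the plan's own figures.**

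- Screening column: 40 + 6 + 5 = 51 mL, exactly the figure in section 1.16. This supports the reading of the table's columns.
- Largest single day: day 0, with 10 serum + 10 plasma + 7.5 RNA + 30 PBMC = 57.5 mL, within the 70 mL daily limit.
- Cumulative limit of 500 mL: met by 496.5 mL if screening is left out, not met by 547.5 mL if it is included.

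**Step 2: size of the gap on each reading.**

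- Screening counted: 547.5 − 500 = 47.5 mL over; 47.5 / 500 = 9.5%.
- Screening not counted: 500 − 496.5 = 3.5 mL of headroom.

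**Step 3: PBMC volumes in the text against the table.** Table 1 lists 10 mL at five draws (days 1, 3, 4, 5 and 14), below the 20 mL lower end in section 1.16. Raising those five to 20 mL adds 5 × 10 = 50 mL:

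- without screening: 496.5 + 50 = 546.5 mL (46.5 mL over);
- with screening: 547.5 + 50 = 597.5 mL (97.5 mL over).

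**Step 4: draws outside Table 1, on the narrower reading.**

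- DNA: any extra draw above 3.5 mL exceeds the limit. Use of leftover blood adds nothing.
- A natural-infection visit before day 28: 10 + 40 = 50 mL, so 496.5 + 50 = 546.5 mL.

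**The case against.** The strongest reply is that section 1.16 totals the screening visit on its own, moves on to the study draws, and only then states the daily and cumulative limits. If the 500 mL covers what follows screening, all three figures agree with Table 1: 51 against 51, 57.5 against 70, and 496.5 against 500. A remainder so close to 500 suggests that the limit was built this way. The 51 mL match, which confirms the reading of the table, equally shows that the authors summed screening separately.

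This stands, and it rules out a stronger claim. A reader might infer that every participant who completes the schedule breaches the limit. That holds only if the screening visit counts, or if the text's PBMC range overrides the table, and the documents settle neither. A reader might also infer that particular samples would be lost or that participants were told the wrong total. The documents do not say which draws, if any, would be dropped, and the participant information is not among them.

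The contingent items also deserve caution. DNA may need no extra draw, and a natural infection before day 28 is possible but is not a scheduled event.

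The reply does not dispose of the PBMC mismatch. The 20 to 40 mL range could be a loose summary that Table 1 overrides, since the same sentence cites the table, but the protocol does not say so. Nor can the range easily be read as all blood on those occasions, because the next sentence describes the other samples as additional.

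**Conclusion.** The point holds as an unresolved inconsistency between section 1.16 and Table 1. It is not a demonstrated breach for every participant. The scheduled total is 547.5 mL (9.5% over) or 496.5 mL (3.5 mL under), depending on whether the 51 mL screening visit counts. If the PBMC range in the text is followed at its minimum, the totals are 597.5 mL and 546.5 mL, and the limit is exceeded on either reading.

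The 500 mL limit therefore holds only if four conditions are all met: screening is excluded; Table 1 governs the PBMC volumes; extra blood for DNA is at most 3.5 mL; and no natural-infection visit occurs before day 28. The protocol states none of these.

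The totals assume that the table's columns survived extraction from the PDF. The 51 mL match supports this, and the sums depend only on which values sit in the pre-screening, screening and day 180 columns. The daily limit is respected. The primary objective, which rests on sensor measurements, is not affected. The matter should still be put right, because it concerns a stated ceiling for healthy volunteers and is cheap to correct.

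**What to change.** Reconcile section 1.16 with Table 1:

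1. State whether the screening visit, any extra DNA draw and any natural-infection visit before day 28 count toward the cumulative limit.
2. Align the PBMC volumes on days 1, 3, 4, 5 and 14 between text and table.
3. Make the stated total equal what the schedule takes under those rules.
4. Check that the participant information carries the same figure.
5. If any volume changes, name the affected draws in advance so that the change is planned and the same for every participant.

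The sponsor decides which figures are right. The cost is a minor amendment and, if the check in item 4 shows a difference, a matching change to the participant information. Depending on the sponsor's choice, there may also be a higher stated total or smaller volumes at some time points.

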1.17. Physical examination, physiological and symptom monitoring devices

1.17.1. Physical Examination will include ENT, respiratory and cardiac assessment, and will be performed by a study doctor at screening and days -7, -1, 0 (prior to inoculation), discharge, 14 and 28 days post inoculation.

The Bittium Faros, Biovotion, and Lumee devices will be given to each participant at the day -7 pre-inoculation visit. They will be fitted as required and the participant will be counselled regarding their positioning, care and data downloads (if appropriate). A mobile telephone (without SIM card) will be provided to each participant with applications for the relevant sensor devices pre-loaded. After completion of the study, all Faros, Biovotion, Lumee patches, study mobile devices and mobile device charging cables will be returned to study personnel.

1.17.2. Bittium Faros sensor

The Bittium (formerly eMotion) 180° Faros sensor monitors heart rate variability, electrocardiography and physical activity. The sensor box (Figure 1) will be attached to the chest with two disposable, adhesive electrodes positioned on the chest. The device is CE-marked (93/42/EEC) and is in accordance with MDD Class IIa. The sensor and electrodes are not waterproof and will need to be removed before showers etc. They are also not suitable to use in an MRI environment. The device is not intended to be used along high frequency surgical equipment or a defibrillator. The device will require charging via docking station and data will be downloaded intermittently via USB cable to a computer by study personnel at study visits. After successful connection of the sensor, study personnel will explain and train subjects on how to use the Faros as well as ensuring study subjects understand usage, handling and maintaining of the device and electrodes. An initial data collection process will be undertaken to check that the Faros is working correctly prior to the end of the study visit.

Figure 1: Bittium Faros sensor and positioning.

1.17.3. Biovotion Everion sensor

The Biovotion Everion (Figure 2) is a CE marked, non-invasive wearable multi-sensor device that monitors heart rate, skin temperature, respiration rate, steps, activity, and energy expenditure from the skin's surface. It will be attached to the left or right upper arm using an armband and will be in contact with intact skin only. All measurements are taken on the surface of the skin. Data from the device is collected via the Biovotion application, which will be pre-loaded to the mobile device provided. Each participant will have a study user account created with identification only by subject study ID. After successful connection of the sensor and mobile device, study personnel will explain and train subjects on how to use the Biovotion Everion and the features of the Biovotion application as well as ensuring study subjects understand usage, handling and maintaining of the Biovotion Everion. An initial data collection process will be undertaken to check that the Biovotion Everion is working correctly prior to the end of the study visit. The following parameters will be collected: activity, barometric pressure barometer temperature, skin blood perfusion index, blood pulse wave, energy expenditure, galvanic skin response, heart rate, heart rate variability, local temperature, skin temperature, respiration rate, blood oxygenation and steps per day.

Figure 2: Biovotion Everion device, charger/docking station and armband positioning.

1.17.4. Profusa Lumee™ Oxygen Platform device

The Profusa Lumee oxygen monitoring device is designed to reliably report tissue oxygen levels and is currently used in clinical practice to monitor the severity of artery narrowing and oxygen delivery to the limbs. The device is in two parts, the sensor and the reader. The sensor is a soft, flexible fibre approximately 5 mm long and 0.5 mm in diameter and is made of a material shown to be biologically compatible with body tissue. It will be injected under the skin at depth of 2-6 mm from the skin surface using a single-use, disposable Lumee Pen injectable device by trained study staff. Previous studies have shown that the Lumee sensor is biologically inert, causes no reaction in the tissues and once inserted can neither be seen nor felt. The sensor reacts with oxygen in the tissue and emits invisible light proportional to the amount of surrounding oxygen. In total, 2 sensors will be inserted (one in the skin of the upper arm and one on the side of the chest). A wireless patch reader is placed on top of the skin over the area where the sensor has been placed to measure local oxygen content. These data are then transferred to the Lumee Patch App on the dedicated mobile device via Bluetooth. When the Lumee is first given to the participant, it will be paired with the Lumee Patch app via Bluetooth. After that, the device will automatically synchronise via Bluetooth with the mobile device. After successful connection of the sensor and mobile device, study personnel will explain and train subjects on how to use the Lumee and the features of the Profusa Lumee application as well as ensuring study subjects understand usage, handling and maintaining of the Lumee. An initial data collection process will be undertaken to check that the Lumee is working correctly prior to the end of the study visit.

The sensor and current version of the wired reader devices are CE Marked for use in the European Union and other countries that accept the CE Mark. The wireless reader that will be used in this study has not yet been received the CE Mark. This certification is in process but this study and data generated will not be used in any CE marking application.

Of note:

- Extensive pre-clinical and clinical studies show that the device causes minimal foreign body, scarring or allergic reactions
- The oxygen sensor contains no electronic components and does not store data
- Once inserted, the oxygen sensor is not visible by the naked eye and is usually not palpable
- Light is emitted from the sensor but is undetectable by eye and readable only by the patch reader
- Data is stored on the patch reader until it is downloaded to the Lumee Patch App, which will be installed on a mobile phone device
- Resulting data will be anonymised before transfer via a desktop computer to a storage server

Please see the [Instructions for Use](#) for full information about this device.

Figure 4: Profusa Lumee and Lumee Pen insertion device.

1.18. Lung Function Tests

At the screening visit and at other visits as described in table 1 in, measurements of FEV1 and FVC will be made as outlined below.

Predicted Values for Lung Function Measurements = the predicted or reference values for lung function measurements are those recommended by the Report Working Party for the European Community for Coal and Steel. Also incorporated are the recommendations of the British Thoracic Society and the Association of Respiratory Technicians and Physiologists.

1.18.1. Measuring FEV₁ and FVC by Spirometry

Performing the measurement:

- Posture must be consistent during a study, either standing or sitting, with no breathing limitation
- The subject should breathe in to total lung capacity. A good tight seal by the lips round the mouthpiece is essential. The subject should then exhale forcibly into the spirometer, blowing as hard as possible and continue to residual volume
- The best value of 3 attempts will be recorded
- Calibration: Vitalograph dry wedge bellows spirometers will be serviced and calibrated at least once every year by an engineer from Vitalograph. However, the calibration will be checked at least once a month using a calibrated one litre syringe.

1.19. Clinical Scores and Cognitive Tests

To assess the impact of infection, a self-completed diary card of upper and lower respiratory tract and systemic symptoms will be provided between day -7 and day 14, and participants will be instructed to complete this prior to inoculation and daily sampling. During the course of the study, 3 computerised

tests of attention will also be performed. Finally, to estimate the impact of social support on their response to infection, participants will be asked to complete two paper questionnaires to assess their social support and impacts, which will be given to them at the beginning of the quarantine period and completed by the participants as soon as possible during their in-patient stay.

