1.11. Study visits

The study is divided into outpatient and confinement phases. Subjects will stay overnight for a period of 8-11 nights in total, from the morning before the viral challenge, to the 8-10th day after viral challenge. This period of confinement has been chosen to eliminate the possibility of subjects in the study transmitting the virus to anyone not involved in the study (i.e. family, household contacts, and the wider community). Confinement is not used to enable closer monitoring or to enhance safety for study subjects, although this may be an additional benefit in some circumstances. During the confinement period, all study procedures will take place in the confinement facility (Table 1). There will also be follow-up visits (1.11.3).

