1.11.2. Confinement period (confinement, day -1 to day 8-10)

On the morning of the day before viral challenge, participants will attend the ICRRU, or ICRF. A single nasal lavage sample will be taken to exclude coincidental infection, breath collection, a nasal SAM and blood will be taken for PBMCs, plasma and RNA. Following this, subject to a satisfactory assessment by the study doctor (brief interview and symptom-directed medical examination), we will infect the volunteers with influenza A/Belgium/4217/2015 at a dose of 5×10^5 TCID₅₀ in a volume of 0,5mL divided between nostrils. After infection, participants will be observed by a member of the study team or ICRF staff member for a period of one hour to ensure no adverse reactions have occurred. They will enter a residential research facility (confinement facility), where they will reside for the next 8-11 nights so we can monitor the development of cold symptoms and collect samples to evaluate immune responses and test the hypotheses. These will include daily blood samples, breath collection, throat swabs, nasal lavage, nasal SAM, nasal scrapes, and lung function tests. Participants will be seen daily by the study team. On the 8th day of residence, assuming all significant symptoms have resolved and at the discretion of the principle investigator, participants will leave the confinement facility and asked to return daily for assessment and sampling, at home they will need to continue their symptom diary only. If symptoms continue or the study doctors deems it necessary, the volunteer will be asked to remain until the 9th or 10th day of residence at which time they will be discharged, subject to a satisfactory assessment by the study doctor. If a subject is discharged before the 10th day or wishes to withdraw after virus inoculation but before the 10th day, we will strongly advise them to confine themselves in their own homes, and to strictly avoid any contact with young children, the elderly or other high-risk individuals for the remainder of the period during which viral shedding may occur. Additionally, subjects infected with influenza withdrawing before the 8th day post-inoculation may be treated with oseltamivir to reduce the risk of viral shedding having left confinement. This will be provided from pharmacy, as agreed with ICRF PRB.

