1.19.6. Social Support Questionnaire and Interpersonal Support Evaluation List

The Social Support Questionnaire is a 27-item questionnaire designed to measure perceptions of social support and satisfaction with that social support. Each item is a question that solicits a two-part answer: Part 1 asks participants to list all the people that fit the description of the question, and Part 2 asks participants to indicate how satisfied they are, in general, with these people. The test is administered as a paper questionnaire (identified only with the participant identification number) and should take approximately 20 to 30 minutes to complete. The test will be administered once during the study, at entry to the quarantine unit. Please see Appendix II for the Social Support questionnaire.

The Interpersonal Support Evaluation List is a 40 point scale made up of 4 sub-scales (tangible support; belonging support; self-esteem support; appraisal support). Participants rate each item's statement on how true or false they believe it is for themselves. All answers are given on a 4-point scale ranging from "Definitely True" to "Definitely False". Please see Appendix III for the Interpersonal Support Evaluation List questionnaire.

ADVERSE EVENTS

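### The social-support questionnaires may be completed after inoculation, even during illness; requiring completion before inoculation would prevent this at almost no cost

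*Combined protocol and SAP*

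**What the plan says.** Section 1.19 (Clinical Scores and Cognitive Tests) gives the purpose of the two questionnaires as "to estimate the impact of social support on their response to infection". Support is therefore the explanatory factor and the response to infection is the outcome. On timing it says two things: the forms are paper questionnaires "which will be given to them at the beginning of the quarantine period", and they are to be "completed by the participants as soon as possible during their in-patient stay".

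Section 1.19.6 adds, for the Social Support Questionnaire only: "The test will be administered once during the study, at entry to the quarantine unit". It gives no time for the Interpersonal Support Evaluation List and describes no repeat of it. Table 1 has a row for the former and none for the latter.

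Social support is not named in the primary, secondary or exploratory objectives (1.3 to 1.5), and the Statistics and Data Analysis section specifies no analysis of it. The synopsis mentions questionnaires in aim 5, as a correlation with sensor measurements and with no direction implied.

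**The concern.** A variable meant to explain the response to infection should be measured before the infection is given. Otherwise an association between low support and severe illness has two readings: poor support made the illness worse, or feeling ill made people report less support. With one administration and no planned repeat, a missed pre-inoculation measurement cannot be recovered, and section 1.10 rules out replacing participants after day 0. The protocol also does not ask for the completion time of these forms, so late ones might not be identifiable at analysis.

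What is at stake is narrow: the interpretation of one ancillary question. The sensor comparisons that carry the primary and secondary objectives do not use these forms.

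**Working it through.** **Step 1. Does the text allow completion after inoculation?**

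- *Length of the stay.* Section 1.11: "Subjects will stay overnight for a period of 8-11 nights in total, from the morning before the viral challenge", ending on day 8-10 after challenge. Most of the permitted window therefore lies after inoculation and covers the expected illness.
- *Start of quarantine.* Section 1.11, the heading of 1.11.2 and the opening of the Study Procedures section ("for days -1 to 10 subjects will reside in the confinement facility and procedures will take place there") all point to day -1. The narrative in 1.11.2, however, describes entry to the residential facility after infection and an hour of observation. Day -1 is the better reading, but entry is not a secure pre-inoculation anchor.
- *Completion deadline.* None is stated for either form. Section 1.19 does tell participants to complete the symptom diary before inoculation, so the authors used that anchor for one instrument and not for these two.
- *Table 1.* Its columns may have shifted in extraction, so nothing here depends on where its marks fall.

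The wording therefore allows completion after inoculation and during illness.

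**Step 2. How large could the effect be?**

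The plan has no figure to reproduce. From the documents: n = 20, and a 75% attack rate, giving 0.75 × 20 = 15 infected. Assumed, because the documents do not say: the number m of forms completed while ill, and the shift k in reported support (SD per SD of severity) on those forms, taken as 0.2, 0.4 or 0.6.

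Model A: severity S ~ N(0,1), true support T ~ N(0,1), independent. Reported support = T − k·S on the m forms completed while ill, and T on the others. The approximate spurious correlation is

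ρ ≈ −k(m/n) / √(1 + k²·m/n).

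For m = 3, k = 0.6: −0.6 × 0.15 / √(1 + 0.36 × 0.15) = −0.09 / 1.027 = −0.088. For m = 5, k = 0.6: −0.15 / √1.09 = −0.144. The simulated mean Spearman correlations are slightly smaller in size: −0.08 and −0.12.

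Model B: 15 infected, with severity gamma (shape 2) scaled to SD 1, and 5 uninfected with severity near 0. Only infected participants can complete a form while ill.

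False-positive rate of a Spearman test at nominal 5%, 20,000 replicates per cell, Monte Carlo standard error √(0.05 × 0.95 / 20,000) ≈ 0.15 points:

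| Forms completed while ill | Model A, k = 0.2 / 0.4 / 0.6 | Model B, k = 0.2 / 0.4 / 0.6 |
|---|---|---|
| 1 | 5.3 / 5.0 / 5.5% | 5.1 / 5.1 / 5.1% |
| 2 | 5.3 / 5.5 / 5.6% | 5.3 / 5.8 / 5.8% |
| 3 | 5.1 / 5.8 / 6.0% | 5.3 / 6.1 / 6.5% |
| 5 | 5.2 / 6.7 / 8.0% | 5.8 / 7.8 / 9.3% |
| 8 | not run | 7.2 / 11.8 / 18.5% |
| 10 | 6.8 / 11.4 / 18.9% | not run |

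With no such forms, Model A returns 4.9 / 5.1 / 5.1%, as it should. With up to three, the worst cell is 6.5%, an excess of 6.5 − 5.0 = 1.5 points. The rows for 8 and 10 forms need many participants to delay until ill, which is unlikely given the instruction to be prompt.

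**Step 3. What would setting late forms aside cost?**

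For an assumed true correlation of 0.5 in size, the Spearman test has power of 57% with 20 forms, 55% with 19, 52% with 18 and 50% with 17.

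**The case against.** The strongest reply is that the plan already describes a baseline measurement. The forms are handed out at the start, promptness is required, and 1.19.6 places the Social Support Questionnaire at entry, the term sections 1.19.4 and 1.19.5 use for the first of three test sessions. A 20 to 30 minute form handled that way would mostly be done before symptoms, and one completed hours after inoculation but before symptoms could not reflect illness.

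The mechanism is also weak. Part 1 of the Social Support Questionnaire lists people, and "Part 2 asks participants to indicate how satisfied they are, in general, with these people", so it does not ask about current state. Quarantine applies to everyone, so isolation alone would not create an association with severity. Finally, no specified analysis tests support against severity, and the size of any influence of illness on answers is assumed.

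Most of this stands, and it is why the point ranks low. It does not close the gap. The entry rule covers one form of two, it fixes when the form is given and not when it must be finished, and entry can itself be read as following inoculation. The absence of a planned analysis also leaves untouched the directional purpose that section 1.19 gives for collecting the data.

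**Conclusion.** The concern holds. The completion rule permits post-inoculation forms for a measure whose stated purpose needs pre-inoculation ones, and no other text prevents it. The practical effect is probably small: at most about 1.5 percentage points of false-positive inflation with up to three forms completed while ill, and more only if many are late and illness moves the answers strongly. Those figures rest on an assumed shift of 0.2 to 0.6 SD per SD of severity and an assumed number of late forms. The sample size, the specified analyses and the primary and secondary objectives are unaffected. This is an optional improvement whose case is its low cost, not a large bias.

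**What to change.** In 1.19, replace the completion rule with a requirement that both questionnaires be completed and collected on day -1, or on day 0 before the inoculum is given. Name inoculation as the anchor, because entry to the unit is ambiguous. Bring 1.19.6 and Table 1 into line, adding a row for the Interpersonal Support Evaluation List. Record the date and time of completion, and flag any form completed after inoculation so that an analysis of support as a predictor can be run with and without it.

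The cost is a few words, one table row and one recorded time. Participants already attend on day -1. The Social Support Questionnaire takes 20 to 30 minutes, and the second form is assumed to be similar. Late forms are kept, so no data are lost; only the sensitivity analysis that omits them gives up a little power.
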